### 8.2.4 Model diagnostics

The fitted primary analysis models will be checked using diagnostic plots based on the standardised conditional residuals. Scedasticity will be assessed by plotting these residuals against the conditional fitted values with a non-parametric locally weighted linear smoothing curve (lowess curve) overlaid.

Normality will be assessed using a quantile-quantile plot. Should these diagnostic analyses suggest serious violation of the model assumptions, then the model described above will be refitted using log-transformed outcome measurements, with a value of 0.1 added prior to transformation to accommodate scores of zero. The fitted model will be used, together with an appropriate transformation, to derive differences in means (at each post treatment time point) on the original scale of measurement, at representative values of the fixed effect covariates in the model (both levels of reference joint, mean of the observed baseline PEM scores and marginalising over the centre random effects).

If serious violation of the model assumptions persists, then the PEM scores at 12 months post-treatment will be modelled in isolation, using a univariate mixed effect linear regression model, adjusting for allocation, reference joint type (the stratification factor) and baseline PEM score as fixed effects, and centre as a random effect. If model assumptions remain violated then an equivalent mixed effect generalised linear model with log link will be fitted. Univariate analyses of the PEM scores at other time points will be conducted in a similar manner.

If model assumptions remain severely violated for the univariate analysis of 12 month PEM scores (using both identity and log links), then a semi-parametric analysis of the untransformed outcome measurements will be conducted using a mixed effect ordinal regression model with logit link. This model will include allocation, reference joint type (the stratification factor) and baseline PEM score as fixed effects, and a random intercept for centre. The adequacy of the logit link will be investigated by assessing the parallelism evident in a plot of the link transformed empirical cumulative distribution function, stratified by randomised group, with a probit link considered if the logit link appears to be severely misspecified. The fitted model will be used to derive estimates of the between group difference in means conditional on representative values of the covariates (both levels of reference joint, mean of the observed baseline PEM scores and marginalising over the centre random effects) together with a two-sided 95% CI based on standard errors obtained via the delta method. Similar analyses will be conducted for PEM scores at other time points.

### **8.2.5 Reporting**

Estimates of the adjusted and unadjusted mean difference between treatments will be obtained at each time point with appropriate two-sided 95% CIs. Estimated differences in mean PEM score over time will be plotted, together with 95% CIs. The primary analysis will be principally concerned with the estimated difference between groups at 12 months post-treatment, with estimates at other time points being considered secondary outcomes. All fixed effect parameter estimates from the fitted primary analysis model will be reported together with their standard errors and Wald 95% CIs. Templates of tables used to report the findings of the primary analysis are given in Appendix E-2.

### **8.3 Further analysis of the primary outcome**

Further analysis of the primary outcome will have two main objectives. Firstly to investigate the robustness of the results of the primary analysis, and secondly to estimate the complier average causal effect (CACE).

### 8.3.1 Missing data

The model used for the primary analysis assumes that missing outcome data are missing at random (MAR) conditional on the fixed effects and non-missing outcomes included in the model. We will use multiple imputation to relax this MAR assumption by imputing missing values conditional on additional pre and post randomisation variables. We will also conduct analyses to investigate the sensitivity of the results to various systematic departures from MAR.

We will initially explore whether there are any obvious patterns of missingness in relation to outcome or baseline characteristics. Reasons for withdrawal and timing of withdrawal will be summarised to examine the extent to which withdrawal is driven by mechanisms plausibly related to outcome and/or treatment allocation. Unadjusted mean PEM score trajectories will be plotted for participants dropping out at each time point (both in aggregate and by allocation).

Associations between key baseline characteristics and missing outcome data and/or withdrawal prior to treatment will be explored using three sets of Firth logistic regression models [9]. Missing values of continuous baseline covariates will be mean imputed when fitting these models. The following baseline characteristics will be assessed

- Age (continuous)
- Sex (male or female)
- Smoking status (current, previous or never)
- Alcohol use (does drink alcohol or doesn't drink alcohol)
- Previous treatment with either limited fasciectomy or collagenase (previous treatment or no previous treatment)
- Presence of comorbidities (Yes or No)
- Number of digits affected (treated as continuous)
- MHQ score (continuous)
- URAM score (continuous)
- EQ-5D general health VAS score (continuous)

The first set of regressions will be used to identify baseline characteristics associated with missing primary outcome data at any post treatment time point. The second will be used to identify baseline characteristics associated with missing primary outcome data at the primary endpoint (12 months) only. The third set will be used to identify baseline characteristics associated with withdrawal prior to treatment. Any baseline variables that are found to improve model fit (compared with the model with all parameters other than the intercept constrained to zero (not omitted)) in a likelihood ratio test of size 10%, will be added as fixed effects to the primary analysis model, and this model refitted. The results of this analysis will be reported in a similar manner to the reporting of the primary analysis (Appendix E-2).

We will also refit the primary analysis model using a multiply imputed dataset. A total of 250 imputations will be generated using multiple imputation by chained equations. The longitudinal structure of the data

will be accounted for by imputing the data in “wide” format. Further clustering by centre will be ignored for the purposes of the imputation model, (given that between centre heterogeneity is expected to be small and is not the focus of the analysis) but will be allowed for in the substantive analysis models fitted to each of the imputed datasets. Imputation will be carried out separately by randomised group to allow for possible interactions between randomised group and other variables included in the imputation model. Only patients that did not withdraw prior to treatment delivery will have their outcome data imputed, although patients that withdrew prior to treatment will be included in the imputation model. Patients who die during follow up will not have outcome data imputed following death. The variables that will be included in the imputation model are given in Table 3. Any baseline variables that are identified as being associated with missingness of post treatment PEM scores and/or non-receipt of treatment (see above) will also be included. Missing values in baseline variables included in the imputation model will be imputed as necessary (with any values imputed via single imputation methods for other analyses removed).

**Table 3:** Details of variables included in the imputation model

Variable	Type	Details	Univariate model (if imputation required)
Post-treatment PEM scores (four time points)	Continuous	Percentage disability (0 – 100)	Predictive mean matching (10 nearest neighbours)
Reference joint	Binary	MCP = 0, PIP = 1	N/A (complete)
Baseline PEM score	Continuous	Percentage disability (0 – 100)	Predictive mean matching (10 nearest neighbours)
Treatment delivery PEM score	Continuous	Percentage disability (0 – 100)	Predictive mean matching (10 nearest neighbours)
Baseline URAM score	Continuous	Integer score between 0 and 45	Predictive mean matching (10 nearest neighbours)
Post-treatment URAM scores (four time points)	Continuous	Integer score between 0 and 45	Predictive mean matching (10 nearest neighbours)
Baseline MHQ score	Continuous	Overall MHQ score between 0 and 100	Predictive mean matching (10 nearest neighbours)
Post-treatment MHQ score (two time points)	Continuous	Overall MHQ score between 0 and 100	Predictive mean matching (10 nearest neighbours)
Passive extension of reference joint at baseline	Continuous	Mean of the available passive extension measurements taken of the reference joint at baseline	Linear regression
Passive extension of reference joint at treatment delivery and 3, 6, 12 and 24 months post-treatment	Continuous	Mean of the available passive extension measurements taken of the reference joint at treatment delivery and 3, 6, 12 and 24 months post-treatment	Linear regression
Active extension of reference joint at baseline	Continuous	Mean of the available active extension measurements taken of the reference joint at baseline	Linear regression
Active extension of reference joint at treatment delivery and 3, 6, 12 and 24 months post-treatment	Continuous	Mean of the available active extension measurements taken of the reference joint at treatment delivery and 3, 6, 12 and 24 months post-treatment	Linear regression
Flexion of reference joint at baseline	Continuous	Mean of the available flexion measurements taken of the reference joint at baseline	Linear regression
Flexion of reference joint at treatment delivery and 3, 6, 12 and 24 months post-treatment	Continuous	Mean of the available flexion measurements taken of the reference joint at treatment delivery and 3, 6, 12 and 24 months post-treatment	Linear regression

Crossover	Binary	Did not receive allocated treatment = 0, Received allocated treatment = 1	Logistic regression (with data augmentation if necessary)
Complications	Binary	No complication = 0, Complication = 1	Logistic regression (with data augmentation if necessary)
Further treatment	Binary	No further treatment = 0, Further treatment = 1. Defined as additional treatment to the reference digit with collagenase, limited fasciectomy, dermofasciectomy or percutaneous needle fasciotomy	Logistic regression (with data augmentation if necessary)

The length of burn in will be determined by examining the trace plots of the chained equations algorithm, with a minimum burn in of 10 iterations being used if this appears to be sufficiently many for the algorithm to reach a stable state for all imputed variables. Imputed datasets will be analysed using the same model used for the primary analysis (without the Kenward-Roger degrees of freedom adjustment) with parameter estimates being combined according to Rubin's rules. The results will be reported in a similar manner to the reporting of the primary analysis results (Appendix E-2)

We will also investigate the sensitivity of results to departures from missing at random by imputing missing primary outcome data under a range of missing not at random scenarios. This will follow a pattern mixture modelling approach as implemented in the user contributed Stata command `rctmiss` [10]. At present this command does not support the covariance pattern model used for the primary analysis. We will therefore only use the outcome data from the 12 month post-treatment time point and use a substantive analysis based on analysis of covariance. Two versions of this analysis will be conducted; one including only patients who did not withdraw prior to treatment, and one including all randomised patients. The substantive analysis models will include allocation, study reference joint and baseline PEM score as predictors, with clustering by centre accounted for using a cluster robust standard error. Imputation will be performed allowing the sensitivity parameter of the pattern mixture model to vary from 0 (mean score among those with missing outcome data is the same as the mean score among those with non-missing outcome data, conditional on the covariates) to +/-10 (mean score among those with missing outcome data is +/-10 points larger/smaller than among those with non-missing outcome data, conditional on the covariates) in each group separately and across both groups. The tabular and graphical summaries used to report the results of these sensitivity analysis are given in Appendix E-2.

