## **2. Design**

DISC is a multi-centre, parallel group, individually randomised controlled non-inferiority trial of collagenase injection and manipulation versus limited fasciectomy surgery for the treatment of Dupuytren's contracture. In addition to the main study, DISC contains a qualitative sub study and a photography sub study. This plan outlines the pre-specified analyses of the main trial and the photography sub study. Eligible and consenting patients will be randomised 1:1 to either collagenase injection and manipulation or limited fasciectomy surgery, using a secure randomisation service. Due to the nature of the interventions under investigation, it is not possible to blind clinicians or participants to their treatment allocation. Both treatments should be delivered within 18 weeks of randomisation (as per referral to treatment time), however where possible sites should deliver treatment within 12 weeks of randomisation. Participants will be followed up at 2 and 6 weeks post treatment and 3, 6, 12 and 24 months post treatment. A flow diagram illustrating the flow of participants through the study is presented in Appendix A.

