### **6.1 Treatment preferences**

Participants are asked about their treatment preferences at baseline. Participants indicate whether they would prefer to receive collagenase, limited fasciectomy or have no preference. The baseline CRF is clear that their response to this question will have no impact on their chances of receiving a particular treatment. This data will be used as part of a subgroup analysis to explore possible treatment effect heterogeneity due to receipt (or otherwise) of the preferred treatment.

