### **8.5.1 Treatment preferences**

Since it is not possible to blind participants to their treatment/allocation and the primary outcome was self-reported, it is plausible that treatment preferences at baseline may influence PEM responses during follow up. The data collected on treatment preferences at baseline will be used to divide participants into three subgroups based on their actual allocation; allocated to preferred treatment, not allocated to preferred treatment and no preference. PEM scores at 12 months post-treatment will be analysed using a univariate linear regression model with fixed effect terms for allocation, reference joint and baseline PEM score and a random intercept for recruitment site, with main effects of preference subgroup (allocated to preferred treatment group, not allocated to preferred treatment group, no treatment preference) and the interaction of this term with allocation being added as fixed effects. This will be compared with the model without this interaction using a likelihood ratio test (both models will be fitted using maximum likelihood). Should this test suggest improvement in model fit at the 10% level, then the model including the preference subgroup main effect and interaction will be used to derive estimates of the treatment effect at 12 months in each preference subgroup together with two sided 95% CIs.

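### Baseline treatment preference is collected and thought to affect PEM, but it cannot enter the missingness screen, the imputation model or the CACE weights

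*SAP*

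**What the plan says.** Section 8.3.1 of the SAP plans a screen of baseline predictors: "Associations between key baseline characteristics and missing outcome data and/or withdrawal prior to treatment will be explored using three sets of Firth logistic regression models". The candidates are introduced by "The following baseline characteristics will be assessed" and are age, sex, smoking, alcohol use, previous treatment, comorbidity, number of digits affected, MHQ, URAM and the EQ-5D VAS. Those that pass a 10% likelihood ratio test are added to the primary model in a refit.

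For the multiple imputation, "The variables that will be included in the imputation model are given in Table 3". That table holds the PEM, URAM and MHQ scores, reference joint, the goniometric measurements, crossover, complications and further treatment. One further route in is given: "Any baseline variables that are identified as being associated with missingness of post treatment PEM scores and/or non-receipt of treatment" are added. In section 8.3.3 the response model behind the CACE weights uses treatment group, reference joint, baseline PEM and the covariates flagged by the same screen.

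On preference, section 6.1 says "Participants are asked about their treatment preferences at baseline", with three answers: collagenase, limited fasciectomy or none. Section 2 says that "it is not possible to blind clinicians or participants to their treatment allocation". Section 8.5.1 says that "it is plausible that treatment preferences at baseline may influence PEM responses during follow up", and uses the variable for a subgroup analysis of 12-month PEM. Appendix D tabulates preference, with a row for missing values, among participants left out of the primary analysis.

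**The concern.** An imputation or response model should include recorded variables that may predict both the outcome and whether it is observed. The SAP itself grants the first link for preference. The second is a reasonable inference in an open trial: someone allocated to the treatment they did not want may be more likely to withdraw or stop returning questionnaires. Section 8.3.1 also sets out to see whether withdrawal is related to allocation, and preference set against allocation bears on that more directly than smoking or alcohol does.

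At stake is how credible the missing-at-random assumption is in three supporting analyses of a non-inferiority conclusion: the covariate-extended model, the multiple imputation and the CACE estimate.

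**Working it through.** **Step 1: can preference enter by any route?**

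| Analysis | How baseline variables enter | Preference possible? |
|---|---|---|
| Covariate-extended model (8.3.1) | The ten screened candidates | No |
| Multiple imputation (8.3.1, Table 3) | Table 3 rows, plus screened candidates | No |
| CACE weights (8.3.3) | Fixed terms, plus screened candidates | No |
| Delta analysis (8.3.1) | Allocation, joint and baseline PEM, with an assumed shift | Only through the shift |

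**Step 2: the plan's own figures, for scale.** Inputs from section 3 are margin 6, SD 22, one-sided 2.5% and 90% power. The normal approximation gives 283 per arm. With the noncentral t, power is 0.8995 at 283 and 0.9005 at 284, so the stated 284 per arm (568) is right, and 568/(1 − 0.20) = 710. The standard error is 22 × √(2/284) = 1.85. The largest point estimate that still shows non-inferiority is 6 − 1.96 × 1.846 = 2.38.

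**Step 3: illustrative bias.** The SAP gives no preference split and no loss by preference, so every input here is an assumption. In one arm let q be the share allocated against their preference, d their excess PEM score, m1 their loss and m0 the loss among the rest.

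- Mismatched share among those observed: s = q(1 − m1) / [q(1 − m1) + (1 − q)(1 − m0)].
- Bias in the observed arm mean: d(s − q).
- Bias in the difference (collagenase − surgery): the first arm's bias minus the second's.

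The ranges tried were d = 3 to 10, m1 = 25% to 40% and m0 = 10% to 15%. Selected results:

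| q collagenase / surgery | d | m1 / m0 | Collagenase arm | Surgery arm | Difference |
|---|---|---|---|---|---|
| 0.3 / 0.3 | 10 | 40% / 10% | −0.78 | −0.78 | 0 |
| 0.1 / 0.5 | 3 | 25% / 15% | −0.03 | −0.09 | +0.06 |
| 0.1 / 0.5 | 10 | 40% / 10% | −0.31 | −1.00 | +0.69 |
| 0.5 / 0.1 | 10 | 40% / 10% | −1.00 | −0.31 | −0.69 |

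For the third row, the surgery arm has s = 0.30/(0.30 + 0.45) = 0.40 and bias 10 × (0.40 − 0.50) = −1.00. The collagenase arm has s = 0.06/(0.06 + 0.81) = 0.069 and bias −0.31. The difference is −0.31 + 1.00 = +0.69. A 60%/10% split gives nearly the same range.

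A positive value counts against collagenase and arises when collagenase is the more preferred treatment. A negative value favours non-inferiority and arises when surgery is. The largest value is 0.69/6 = 11.5% of the margin. In the last row, a true difference of 2.38 + 0.69 = 3.07 would on average be estimated at the 2.38 cut-off.

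**Step 4: does the delta grid span such loss?** With q = 0.5, losses of 40% and 10%, and d = 10, the mismatched are 0.20/0.25 = 80% of the missing and 40% of the observed, a gap of 0.40 × 10 = 4.0 points. With losses of 30% and 10%, and d = 5, the shares are 75% and 43.75%, a gap of 1.6 points. Provided preference is unrelated to joint and baseline PEM, both lie inside the planned range of ±10 by arm.

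**The case against.** The strongest reply is that the plan already handles this loss. The delta analysis shifts the missing scores by up to 10 points in each arm separately, and one version includes all randomised patients, so it also reaches those who withdrew before treatment. A reader might infer from the omission that no planned analysis can address preference-related loss. Step 4 shows that this is not so. What stands against the reply is that the delta analysis varies an assumed shift; it does not learn from a variable on file.

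A reader might also infer that the bias runs in opposite directions in the two arms. It is the preference category at risk that differs: surgery-preferrers in the collagenase arm, collagenase-preferrers in the surgery arm. If mismatched participants do worse and are lost more often, both observed means are too low and the biases offset in the difference. The 1.0-point shift, one sixth of the margin, is a one-arm extreme and not the bias in the treatment effect.

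The figures in step 3 are also crude. The primary model conditions on baseline PEM and on PEM at other visits. The imputation adds URAM, MHQ, goniometry, crossover, complications and further treatment. Partial responders therefore carry some of the preference effect already, and only a remainder is left.

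Finally, the SAP nowhere says that preference drives withdrawal; that link is inference. Section 8.5.1 and Appendix D do look at preference, but the first is a subgroup analysis of the outcome and the second is descriptive. Neither corrects for loss.

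**Conclusion.** The omission is confirmed by the text, and the SAP's own statement about PEM is reason enough to close it. The point is limited to the covariate-extended model, the multiple imputation and the CACE weights. No figure in the SAP is wrong and the primary analysis does not change.

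The bias in the difference is near zero if preferences are balanced and loss is similar across arms. Under the assumed lopsided splits it is about 0.06 to 0.7 points and can favour either arm. These are complete-case figures on inputs that the SAP does not give.

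It would be too strong to conclude that the non-inferiority result is exposed to an untested threat, or that changing Table 3 repairs loss before treatment. Section 8.3.1 does not impute outcomes for patients who withdrew before treatment, so for them the all-randomised delta analysis remains the relevant check.

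**What to change.** 1. Add preference (collagenase, surgery, none) to Table 3 unconditionally, whatever the 10% test shows, with a multinomial logistic model for missing values. Imputation is already run separately by arm, so a main effect is enough to distinguish matched from mismatched allocation. This helps with post-treatment loss.
2. Add preference to the candidate list in section 8.3.1. In the Firth response models enter it with allocation and their interaction, because a pooled main effect could cancel across arms. Test its 2 + 2 = 4 parameters jointly against a model with allocation alone.
3. Carry the same terms into the response model for the CACE weights in section 8.3.3. If the interaction also enters the covariate-extended outcome model, report the treatment difference averaged over the pooled preference distribution, so that it remains comparable with the primary estimate.

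The cost is SAP wording, one categorical imputation step and a few extra terms. No new data are needed, and the sample size and primary analysis stay as they are.

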##### **5.1 Patient Evaluation Measure**

The PEM [1] is a validated 19 item patient reported outcome measure comprised of three parts.

- Part 1 is comprised of 5 items which ask the participant about their experience of treatment and the care they received.

- Part 2 is comprised of 11 items which ask the participant about their hand's functionality and any pain they may experience.
- Part 3 is comprised of 3 items and provides an overall assessment of the participant's feelings about their hand condition and treatment.

The participant assigns each item an integer score between 1 and 7, where higher scores indicate worse outcomes/experiences. Participants complete the PEM at baseline, immediately prior to treatment delivery and at 3, 6, 12 and 24 months post treatment. Participants are instructed to complete the PEM with respect to the hand designated as the study reference hand. PEM data will be scored as follows.

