## **5.2 Unité Rhumatologique des Affections de la Main Scale**

The URAM is a validated, 9 item, disease specific disability scale assessing the difficulty experienced by the participant in performing particular tasks or movements [2]. Each item is scored between 0 and 5 with higher scores indicating greater difficulty. Participants complete the URAM at baseline and 3, 6, 12 and 24 months post treatment.

- If more than two items are missing then an overall URAM score cannot be calculated and should be considered missing.
- If the participant has fewer than three missing items, then any missing items are imputed with the mean of the non-missing items. If a participant has more than two missing items, then an overall score is not calculated and is considered missing.
- The overall score is calculated by summing the scores for all nine items. The resulting score should be between 0 and 45 with higher scores indicating greater difficulties.

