## **5.3 Michigan Hand Questionnaire**

The MHQ is a validated, 63 question measure featuring 6 domains: overall hand function, activities of daily living, work performance, pain, aesthetics and patient satisfaction with hand function [3, 4]. Each item is scored between 1 and 5, with some items pertaining to a specific hand and some pertaining to both hands.

The MHQ can be used to generate 7 scale/summary scores for the left hand, right hand and for both hands, giving a total of 21 different summary scores as follows;

- 3x Overall Function scale scores
- 3x Activities of Daily Living scale scores
- 3x Work scale scores
- 3x Pain scale scores
- 3x Aesthetics scale scores
- 3x Satisfaction scale scores
- 3x Overall MHQ scores

Analysis of this data will be concerned with the 6 scale scores and overall MHQ score calculated for the reference hand. Participants complete the MHQ at baseline and 12 and 24 months post treatment. The scoring procedure for the MHQ is given in Appendix C.

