#### **5.4 Single Assessment Numeric Evaluation**

SANE [5] is a single patient reported numerical assessment of hand function, provided by means of a visual analogue scale (VAS). Participants are asked the following question

*How would you rate your hand function today (with normal being 100%)?*

Participants respond by marking a single point on a line between 0 and 100%, to indicate the extent to which they perceive their hand function as being normal. A SANE score is collected at baseline, 2 and 6 weeks post treatment and 3, 6, 12 and 24 months post treatment.

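### The imputation model omits SANE, the only hand-function score at 2 and 6 weeks, so treated participants lost before 3 months are imputed without any early patient-reported hand outcome

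*SAP*

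**What the plan says.** Section 8.3.1 gives the purpose of the imputation: "We will use multiple imputation to relax this MAR assumption by imputing missing values conditional on additional pre and post randomisation variables". It then fixes the content: "The variables that will be included in the imputation model are given in Table 3". Table 3 lists PEM, reference joint, URAM, MHQ, passive and active extension, flexion, crossover, complications and further treatment. SANE is absent at every time point.

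There is one route for extending the list: "Any baseline variables that are identified as being associated with missingness of post treatment PEM scores and/or non-receipt of treatment (see above) will also be" brought in. The ten baseline candidates named in section 8.3.1 do not include SANE, and a 2- or 6-week score is not a baseline variable in any case.

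Section 5.4 describes the omitted measure: "SANE [5] is a single patient reported numerical assessment of hand function". Its schedule is the fullest of the hand scores: "A SANE score is collected at baseline, 2 and 6 weeks post treatment and 3, 6, 12 and 24 months post treatment".

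**The concern.** Section 8.1 limits the primary model to participants with at least one post-treatment PEM score. A participant who is treated, returns the 2- and 6-week forms and is then lost contributes nothing to it. The multiple imputation is one of the few analyses that brings this participant back, and it is meant to do so with extra post-randomisation data.

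Early recovery could plausibly influence both dropout and the 12-month score, and it may differ between an injection and an operation. If so, an imputation that does not condition on early hand function assumes missing at random given less than the trial has collected. At stake is how convincing this sensitivity analysis is for early dropouts. The same applies to the recurrence, range of movement, active extension and flexion analyses (sections 8.4.7 to 8.4.10), which reuse the imputed datasets.

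**Working it through.** **Schedules side by side (sections 5.1 to 5.6, 5.11 and Appendix B)**

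- PEM: "Participants complete the PEM at baseline, immediately prior to treatment delivery and at 3, 6, 12 and 24 months post treatment". Nothing at 2 or 6 weeks.
- URAM: "Participants complete the URAM at baseline and 3, 6, 12 and 24 months post treatment". Nothing at 2 or 6 weeks.
- MHQ: "Participants complete the MHQ at baseline and 12 and 24 months post treatment". Nothing before 12 months.
- Extension and flexion: first post-treatment values at 3 months. The treatment-delivery extension values in Table 1 are pre-treatment.
- EQ-5D-5L: collected at 2 and 6 weeks, but it measures general health, and its post-treatment scores are not in Table 3 either.
- SANE: collected at 2 and 6 weeks, not in Table 3.

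For a participant lost between 6 weeks and 3 months, every repeated post-treatment score in Table 3 is missing. What remains is baseline and pre-treatment data and three binary indicators. Early patient-reported hand scores used: 0. Available: up to 2.

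**Other planned PEM analyses.** The missing-not-at-random analysis conditions on allocation, reference joint and baseline PEM. The weights in section 8.3.3 use allocation and baseline covariates. Neither uses an early outcome.

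**Size of Table 3.** PEM 4+1+1 = 6; reference joint 1; URAM 1+4 = 5; MHQ 1+2 = 3; passive extension, active extension and flexion (1+5) each = 18; binary indicators 3. Total 6+1+5+3+18+3 = 36, with 710/2 = 355 participants per arm at the target.

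**The plan's own figures (context only).** With margin 6, SD 22, one-sided 2.5% and 90% power, the exact t calculation gives 284 per arm (power 0.9005), and 568/0.8 = 710. Both reproduce. The point does not depend on them beyond the SD and the margin.

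**Illustration on assumed values.** The SAP gives no figure for this point. Assume:

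- 12-month PEM correlates 0.40 with baseline PEM and 0.45 with pre-treatment PEM, and those two correlate 0.75;
- 6-week SANE correlates -0.30 with each of those two, and r = -0.3 to -0.6 with 12-month PEM;
- PEM SD is 22.

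1. Explained variance without SANE: (0.40² + 0.45² - 2×0.40×0.45×0.75)/(1 - 0.75²) = 0.0925/0.4375 = 0.211.
2. Overlap of SANE with the two PEM scores: 2×0.30²/1.75 = 0.103, leaving 0.897. Part of r already carried by them: -0.30×0.85/1.75 = -0.146.
3. Standardised partial coefficient b = (r + 0.146)/0.897, which is -0.172 at r = -0.3 and -0.506 at r = -0.6.
4. Explained variance with SANE: 0.211 + b²×0.897 = 0.238 to 0.441.
5. If early dropouts have SANE 0.5 to 1 SD worse than their other data predict, each imputed PEM is too favourable by |b|×shift×22: from 0.172×0.5×22 = 1.9 to 0.506×1×22 = 11.1 points.
6. With 5-10% of one arm lost this way, the arm mean moves from 0.05×1.9 = 0.09 to 0.10×11.1 = 1.1 points.

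A simpler version assumes 5-10% lost per arm, SANE 5-10 points off expectation and 0.3-0.5 PEM points per SANE point. Opposite shifts in the two arms give 0.05×0.3×10 = 0.15 to 0.10×0.5×20 = 1.0. A shift in one arm only gives 0.05×0.3×5 = 0.075 to 0.10×0.5×10 = 0.5. Equal shifts in the same direction give 0.

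**The case against.** The strongest reply is that this cannot change the trial's conclusion. Section 8 bases non-inferiority on the primary model, and adding SANE to Table 3 leaves that model untouched. This stands. A reader might turn a bias of 0.15 to 1.0 points into a one-sided error at the margin: with SE = 22×√(2/284) = 1.846, Φ(-1.96 + bias/1.846) is 3.0% to 7.8%. The SAP does not support that reading. The omission does not cause such an error in the primary analysis, adding SANE would not reduce it there, and the range needs opposite shifts in the two arms.

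Second, section 8.3.1 already shifts missing 12-month PEM by up to ±10 points, in each arm separately and in both. A shift of 10 in one arm moves its mean by 1.0 point at 10% missing and by 2.0 at the 20% attrition assumed in section 3. Effects of the size illustrated are therefore essentially covered; only the extreme per-participant value of 11.1 lies just outside. This largely stands, although the grid shows what a given shift would do and not which shift the collected data support.

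Third, a reader might infer that the imputation knows nothing of early recovery. That is too strong. Complications draw partly on adverse event reporting (section 8.4.11), which Appendix B allows at 2 and 6 weeks, so a poor early course can enter, though only as yes or no.

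Fourth, the choice of auxiliary variables is discretionary, and Table 3 does include many post-randomisation ones. That is fair, but for the early dropouts almost all of them are missing.

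**Conclusion.** The omission is real and worth correcting, as an improvement to a sensitivity analysis. For treated participants lost before 3 months, Table 3 supplies no early patient-reported hand outcome although the trial collects one, which falls short of the stated aim of the imputation.

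Its size is not known. Under the assumptions shown, it is about 0.1 to 1 PEM point in the imputed analysis, against a 6-point margin. It could be zero or run in favour of either arm. It rests on assumed correlations and on 5-10% of an arm being lost after returning an early form. The SAP does not state that share; it would be a quarter to a half of the 20% attrition assumed at 12 months. Participants lost before week 2 would gain nothing. The benefit to the joint-outcome analyses has not been quantified. The primary estimate, its confidence interval and its error rate are unaffected.

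**What to change.** Add SANE at baseline, 2 weeks and 6 weeks to Table 3, imputed by predictive mean matching with 10 nearest neighbours like the other scores there. Add SANE at 3, 6, 12 and 24 months if the trace plots show that the chained equations remain stable. The later scores matter less, because URAM is collected at the same visits and is already included.

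No new data are needed and the primary model does not change. The cost is three to seven variables on top of 36, in an imputation run separately by arm and already carrying substantial missing goniometric data. Collinearity and convergence therefore need watching, and the SAP should say in advance that the three-variable version is the fallback.
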